Therefore, we propose to provide structural group educations focus on accurate BP measurement, provided with validated home BP device, with regular reassessment of BP measurement technique. We are interested to find out whether the proposed intervention can lower BP and sustain high quality HBPM.

Study Aims and Objectives:

We aims at comparing providing validated home BP device, followed by group education of self-BP monitoring and regular assessment accuracy of BP monitoring, which may possibly improve BP control rate of patients with uncontrolled hypertension in primary care setting. We would also like to evaluate whether the quality of BP measurement is sustainable, any change in biochemical markers, clinic BP readings in 6 months, 12 months and 18 months interval. We would also find out patients' view on home BP monitoring and the education program.

Research Questions

1. Do the people with uncontrolled BP have higher control rate after provision of validated BP device followed by education and assessment of BP measurement technique?
2. Are there improvements in the clinic BP body weight, BMI, biochemical markers followed by the HBPM education program?
3. Can quality of HBPM be sustainable by education followed by regular reassessment?
4. What is patients' view on HBPM?

Methods

We adopt prospective longitudinal randomized control trial. Subjects from four general outpatient clinics (GOPCs) located in urban residential area will be involved in the study.

Study Practices and randomization procedure

We aimed to determine the effectiveness of HBPM education and provision of validated home BP device. Since the intervention involve doctors, nurses and patient cooperation, cluster (using one clinic as one cluster) approach is utilized to minimize risk of treatment contamination. Three clinics are randomly assigned as intervention clinic and the other three will be assigned as usual care clinic. (Appendix 1) To avoid contamination, separate protocols will be sent to individual clinics assigned to intervention and control. The Research helper will assist subject recruitment and data collection. The measurements and lab test will be performed by local clinic nurses and doctors in control clinics.

Research Subjects Recruitment

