The recruitment of subjects and study workflow is shown in **Figure 1**. We include adult subjects aged above 18 years old on hypertensive treatment more than 12 months with uncontrolled hypertension and no previous HBPM on the day of recruitment. Uncontrolled hypertension is defined as BP > 140/90mmHg(19,20) in subjects age < 80; and BP > 150/90mmHg(21) in subjects age ≥ 80 . They will be invited to participate if they are willing and capable to perform home BP monitoring by themselves on daily basis. Appropriate subjects will be identified during doctor consultation and nurse consultations and subjects will be invited after normal consultation.

We exclude subjects who are unable to perform the home monitoring either by themselves; or have arrhythmias, unstable angina, serum creatinine > 250 mmol/l, orthostatic hypotension, severe left ventricular impairment, severe aortic stenosis and pregnancy.

Data Collection

Subjects enrollment and baseline assessment take place before randomization. Follow up data collection will be conducted 6 months, 12 months and 18 months after intervention.

Baseline Assessment

At baseline, patient age, sex, smoking habits, body mass index, waist circumference, education level, occupation, payment method, household income and number of household family members, health literacy by Chinese Health Literacy Scale for Chronic Care (22) will be collected via questionnaires by clinic nurses and research helper. Medical history includes diabetes mellitus, nephropathy, manifest cardiovascular disease (namely ischaemic heart disease, cerebral vascular disease, and peripheral vascular disease), current medication including antihypertensives drugs, lipid lowering agents, and antiplatelet drugs, laboratory test results including fasting blood sugar, glycemic haemoglobin level, lipid profile, serum creatinine level, presence of significant proteinuria will be collected by investigators via computerized patient record.

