Clinic nurses will assess the self-monitoring technique, home BP records, body weight and BMI and the clinic BP levels

4. 18 months post intervention

The above measurement will be collected via questionnaires by clinic nurses and research helper. Medical history includes diabetes mellitus, manifest cardiovascular disease (namely ischaemic heart disease, cerebral vascular disease, and peripheral vascular disease), current medication including antihypertensives drugs, lipid lowering agents, and antiplatelet drugs, laboratory test (6 to 18 months post intervention) results including fasting blood sugar, glycemic haemoglobin level, lipid profile will be collected by investigators via computerized patient record.

Data analysis

The Outcome Measurement includes

1. Blood pressure control rate (Primary outcome)
2. Change in clinic mean systolic and diastolic BP between baseline and each of the follow up point
3. Accuracy of HBPM by standard checklist in 1-3 months and 9-12 months post-intervention
4. Practice of HBPM 6-months post-intervention
5. Change in biochemical markers

6. Change in Body Weight and BMI
7. Adverse effect (reported by research subjects)

Sample size calculation will be based on the mean difference in blood pressure between intervention and controls at 9-12 months after baseline. Accounting for the clustering effect by practice, the intraclass correlation (ICC) for the intra-cluster correlation in primary care setting was taken as 0.01 which was a median estimate reported in previous study (24). In order to have 80% power and 5% false positive error to detect a difference in blood pressure of 3mmHg with assumed standard deviation of 5mmHg, there will be 216 subjects (25) which will be obtained by sampling 6 general outpatient clinics randomly, with 36 subjects each clinic in intervention group and 36 subjects each clinic in control group. Assuming 20% of attrition rate for 6-12 months follow-up, we need to recruit 45 subjects in each group per clinic at baseline, in total of 270 subjects.

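### The only power statement (216 analysed, 80%) is for a 3 mmHg difference in mean blood pressure, so it does not describe the primary outcome, the control rate

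*Protocol*

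**What the plan says.** In the Data analysis section of the Protocol, the first listed outcome is "Blood pressure control rate (Primary outcome"). The second is "Change in clinic mean systolic and diastolic BP between baseline and each of the follow up point". The Research Questions section opens with the same binary target as the primary outcome: "Do the people with uncontrolled BP have higher control rate after provision of validated BP device".

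The sample size paragraph, also under Data analysis, uses the continuous measure: "Sample size calculation will be based on the mean difference in blood pressure between intervention and controls at 9-12 months after baseline". Its inputs are "80% power and 5% false positive error to detect a difference in blood pressure of 3mmHg with assumed standard deviation of 5mmHg" and an ICC of 0.01. It arrives at 216 patients in six clinics of 36, raised to 270 (45 per clinic) for 20% attrition. It does not say whether systolic or diastolic pressure is meant.

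The Protocol gives no expected control-arm rate, target difference or power for the control rate. The Data analysis section assigns dichotomous outcomes a logistic-link GEE and continuous outcomes an identity-link GEE, so it treats the two as separate analyses.

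**The concern.** The primary outcome and the sizing outcome are different quantities. The control rate reduces each patient's pressure to controlled or not controlled, and this generally discards information. A sample that just reaches 80% for a mean difference will therefore usually fall short of 80% for the control rate under the same underlying effect.

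The cost comes at interpretation. If the control-rate comparison is not significant, a reader who looks for the planned power finds one figure, 80%, calculated for something else. The reader cannot tell from the text what control-rate difference the trial was able to detect.

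This is not a matter for an analysis plan. The Protocol itself fixes both the primary outcome and the basis of its size.

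**Working it through.** **Inputs from the Protocol.** Difference 3 mmHg, SD 5 mmHg, ICC 0.01, power 80%, alpha 5%, and 36 analysed in each of six clinics (Data analysis). Three clinics per arm (Study Practices and randomization procedure). Two-sided testing is assumed.

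**Step 1: reproduce 216.** With k = 3 clinics per arm and m = 36:
- Design effect = 1 + (36 − 1) × 0.01 = 1.35.
- SE = 5 × √(2 × 1.35 / 108) = 0.7906 mmHg.
- Noncentrality = 3 / 0.7906 = 3.795.
- Two-sided t with 2(k − 1) = 4 df: power 80.65%. The large-sample normal reference gives 96.7%.
- At m = 35, power on 4 df is 79.9%.

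So 36 is the smallest clinic size that reaches 80%, 6 × 36 = 216, and 216 / 0.8 = 270. Of the methods tried, only this one returns 216: the unclustered formula gives 88 in total, and 120 with the design effect applied. The stated figure is correct for mean blood pressure and leaves almost no margin.

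**Step 2: apply the same method to the control rate.** Assumptions not in the Protocol: binary ICC 0.01, one visit, no gain from covariates or repeated measures, control-arm rate p0 from 10% to 70%. For an intervention rate p1,

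SE = √[(p0(1 − p0) + p1(1 − p1)) × 1.35 / 108], where 1.35 / 108 = 0.0125.

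(a) *Difference detectable with 80% power.* This needs no assumed shift in blood pressure. On 4 df the difference must be about 3.76 SE. Example at p0 = 0.40: p1 = 0.684 gives SE = √(0.4561 × 0.0125) = 0.0755, and 0.284 / 0.0755 = 3.76.

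(b) *Power if the Protocol's 3/5 = 0.6 SD shift acts on one normally distributed pressure with a single cut-off.* Then p1 = Φ(Φ⁻¹(p0) + 0.6). Example at p0 = 0.40: p1 = 0.636, SE = 0.0768, 0.236 / 0.0768 = 3.07, and power on 4 df is 63.8%.

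| p0 | Detectable difference, 4 df (points) | Large-sample (points) | p1 at 0.6 SD | Power, 4 df | Power, large-sample |
|---|---|---|---|---|---|
| 10% | 24 | 17 | 24.8% | 48.1% | 71.0% |
| 20% | 27 | 20 | 40.5% | 58.9% | 82.4% |
| 30% | 28 | 21 | 53.0% | 63.0% | 85.9% |
| 40% | 28 | 22 | 63.6% | 63.8% | 86.6% |
| 50% | 27 | 21 | 72.6% | 62.3% | 85.4% |
| 60% | 25 | 20 | 80.3% | 58.7% | 82.2% |
| 70% | 22 | 18 | 87.0% | 52.6% | 76.0% |

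**Step 3: sensitivity.** On 4 df with the 0.6 SD shift, power peaks at about 64% whatever the control-arm rate. With a binary ICC of 0 it peaks at about 76%. With a shift of 0.3 SD it is 15-22%, and with 0.8 SD it is 73-86%.

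**The case against.** The sample size paragraph says openly that it rests on mean blood pressure, and sizing on a continuous measure is common. That stands: the Protocol nowhere claims 80% power for the control rate, and a reader who infers such a claim goes beyond the text. But sizing on another measure needs a reason and a link to the primary outcome, and neither is given.

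A reader might also infer that the trial is shown to be underpowered. The document does not support this. Every control-rate figure above needs inputs that the Protocol does not give. The single cut-off in (b) simplifies a joint, age-dependent definition: "Uncontrolled hypertension is defined as BP > 140/90mmHg(19,20) in subjects age < 80", with 150/90 from age 80. On the large-sample reference, five of the seven control-arm rates exceed 80%. The planned GEE uses repeated measurements and baseline characteristics, and any gain from these is left out. Against that, 4 df is the basis on which 216 reproduces, and further visits add no clinics. Like for like, the control rate has less power than mean blood pressure on both references.

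Nor is it right that nothing can be judged: the number of patients, the clinics and the ICC are stated, and (a) adds only a control-arm rate and a binary ICC.

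The timing looks like a further conflict: sizing is at 9-12 months, the primary analysis at 6-18 months, and "Follow up data collection will be conducted 6 months, 12 months and 18 months after intervention". This is secondary, because a 12-month visit fits all three. Finally, the sizing measure is of the same kind as outcome 2 but not identical to it: outcome 2 is change from baseline, for both pressures, at each follow-up.

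**Conclusion.** The concern holds in this form: the 80% does not describe the primary comparison, and no power is stated for it. The 216 and 270 are correct for what they claim.

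Under the assumptions listed, 80% power for the control rate needs a difference of about 22-28 percentage points on 4 df, or 17-22 on a large-sample reference that ignores having only six clusters. Carrying over the 0.6 SD shift gives about 48-64% (71-87% large-sample), against 80.7% (96.7%) for mean blood pressure. These ranges show that the 80% does not transfer; they are not an estimate of the trial's power.

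A reader might conclude that mean blood pressure should become the primary outcome. The mismatch alone does not justify that: the aims and research question 1 are both framed on the control rate.

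**What to change.** Keep the control rate as the primary outcome and revise the sample size paragraph:

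1. State that the 80% applies to mean blood pressure only, and name systolic or diastolic.
2. Add the power and the detectable difference for the control rate with the existing 216 analysed, over a stated range of control-arm rates and with a stated ICC for the binary outcome.
3. Tie that calculation to one scheduled visit, for example 12 months.
4. Use a method that allows for six clusters.

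The cost is one added calculation and some rewording, plus a stated power for the primary outcome that is probably below 80%. The restatement itself needs no added patients. Whether the sample is then judged sufficient is a separate decision, which the added calculation would inform.

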Descriptive statistics including mean, standard deviation of continuous outcomes and proportion of dichotomous outcomes will be calculated. Primary analysis will be an intention-to-treat analysis of the difference in outcomes between groups at 6-18 months after baseline. As with repeated measurement for patients, generalized estimating equation models using identify link will be conducted to assess differences in continuous outcomes within-group and between groups, adjusting for baseline patients' characteristics and clustering of patients per practice. Generalized estimating equation models using logistic link will be conducted to analyze differences within-group and between groups for dichotomous outcomes, adjusting for same sets of patients' characteristics. Missing values will be imputed using last value carrying forward method. Repeated analysis will be done for per-protocol analysis.

All statistical analyses will be performed using SPSS Windows 21.0 program. P-value less than 0.05 will be considered statistically significant.

Data collection throughout the trial

Demographic Questions	Measurements
Duration of HT	BMI (BH/ BW)
Past Medical history	Waist circumference
Contra-indications to antihypertensive drugs	Clinic BP (sitting position/ standing position)
Current HT medication	Lab Test: FBS, Lipid profile, eGFR, Urine PCR
	HBPM Technique

Qualitative Study on Evaluation of the Programme

Individual interviews (30-45 minutes) to 30 subjects from intervention group will be performed 2-4 months after education seminar and 1st doctor consultation (whenever later). Views on the self-monitoring, home BP reading interpretation blood pressure treatment targets, will be collected.

Sampling Method: 30 subjects with uncontrolled hypertension, some have attended intervention group, with different sex, age group, health literacy and occupations will be interviewed.

Semi-structured interview guide for patients and their family caregivers using social cognitive theory(26) as framework

Framework	Interview questions
Overall experience & attitude	Does high blood pressure (BP) border you? Why? Tell us about your general impression on Self-blood pressure monitoring (SBPM)

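### With only three clinics randomised per arm, the planned GEE at P<0.05 has no small-sample method; run in its usual forms its true error is roughly 9–18%

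*Protocol*

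**What the plan says.** **Design.** Under Study Practices and randomization procedure, the Protocol makes each clinic a cluster and states: "Three clinics are randomly assigned as intervention clinic and the other three will be assigned as usual care clinic". The Methods paragraph just above gives another count: "Subjects from four general outpatient clinics (GOPCs) located in urban residential area will be involved in the study".

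**Analysis.** The Data analysis section names blood pressure control rate as the primary outcome. Its modelling paragraph opens with "As with repeated measurement for patients" and sets identity-link GEE for continuous outcomes, adjusted for baseline characteristics and "clustering of patients per practice". For binary outcomes it says "Generalized estimating equation models using logistic link will be conducted to analyze differences within-group and between groups for dichotomous outcomes", and carries over only the patient characteristics. The threshold is "P-value less than 0.05 will be considered statistically significant", and the software is SPSS 21.0.

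**Sample size.** The same section takes an ICC of 0.01, 80% power and 5% error, and says that to "detect a difference in blood pressure of 3mmHg with assumed standard deviation of 5mmHg, there will be 216 subjects". These come from six clinics with 36 patients each.

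**The concern.** The arm effect is a comparison between clinics, so with three clinics per arm it has at most 4 degrees of freedom, however many patients are enrolled. The usual GEE Wald test relies on having many clusters. With six, the sandwich variance is too small on average, and the normal reference ignores how poorly that variance is estimated.

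If the patient is the GEE subject instead, between-clinic variation is left out of the standard error altogether. The opening reference to repeated measurement permits that reading, and the binary-outcome sentence does not mention clinics.

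At stake is the primary test. In either form the p-value is too small and the confidence interval too narrow, so a result at p<0.05 would not carry a 5% error rate.

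**Working it through.** **Inputs from the Protocol:** K = 3 clinics per arm, m = 36 analysed patients per clinic, ICC 0.01, difference 3 mmHg, SD 5 mmHg, 80% power, 5% error. Two-sided testing is assumed, because sidedness is not stated.

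**1. Reproducing 216**
- Design effect: 1 + 35×0.01 = 1.35.
- SE of the difference: 5×√(2×1.35/(3×36)) = 0.791, so the noncentrality is 3/0.791 = 3.79.
- Two-sided t test on 2(K−1) = 4 df: power 80.7% at m = 36 and 79.9% at m = 35. So 36 is the smallest clinic size that reaches 80%, and 6×36 = 216.
- A normal reference needs only 17 per clinic, and t on N−2 df needs 18. At 36 per clinic the normal calculation gives 96.7%.

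The stated size therefore fits a 4-df test. The Protocol does not say so; this is an inference from the match.

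**2. Clinic as cluster, uncorrected sandwich** (equal clinics, unadjusted continuous outcome; exact)
- The sandwich variance averages (K−1)/K = 2/3 of the correct value, so the Wald statistic is a t(4) variable times √(3/2).
- Normal reference: P(|t4| > 1.96×√(2/3)) = P(|t4| > 1.600) = **18.5%**.
- t(4) reference, variance still uncorrected: P(|t4| > 2.776×√(2/3)) = P(|t4| > 2.267) = 8.6%.
- Unbiased variance, normal reference: P(|t4| > 1.96) = 12.2%.
- Two clinics per arm, uncorrected, normal reference: P(|t2| > 1.96×√(1/2)) = P(|t2| > 1.386) = 30.0%.

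**3. Patient as subject**
- One visit: 2×(1−Φ(1.96/√1.35)) = **9.2%**.
- Three visits: with an assumed within-patient correlation w, the ICC of a patient's mean is 0.01/(0.01 + 0.99×(1+2w)/3). For w = 0.7 this is 0.0125, design effect 1.44, error 10.2%. For w = 0.5 it is 0.0149, design effect 1.52, error 11.2%.
- At an assumed ICC of 0.05, which is not a Protocol value, the one-visit design effect is 2.75 and the error 23.7%. At ICC 0 it is 5%.

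**4. Simulation for the binary outcome** (4,000 runs, no true effect; one visit, ICC 0.01, independence working correlation; assumed 40% control and three covariates with log-odds 0.3 each)

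| Test | 36 per clinic | Unequal clinics (20, 36, 52 v 25, 36, 47) |
|---|---|---|
| Clinic sandwich, z | 17.8–18.0% | 19.3% |
| Patient as subject, z | 8.6% | – |
| Clinic sandwich, t(4), uncorrected | 8.2% | – |
| Sandwich variance × 6/4, t(4) | 4.8% | 5.3% |
| Kauermann-Carroll, t(4) | 4.7% | 5.0% |
| Mancl-DeRouen, t(4) | 2.2% | – |
| Two-stage t test, 4 df | 4.9% | 4.4% |

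A separate simulation with three visits (2,500 runs per setting; assumed 40% control and within-patient latent correlation of 0.5; 0, 4 or 8 covariates) gave, at ICC 0.01, 17–20% for the clinic sandwich with z and 12–14% for patient as subject.

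**5. Interval width.** The correct interval relative to the uncorrected sandwich with z is 2.776/1.960×√1.5 = 1.73 times as wide.

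**The case against.** The strongest reply is that variance estimators, reference distributions and small-sample corrections are ordinary SAP content. The Protocol does not require an uncorrected sandwich or a normal reference, and GEE at P<0.05 is compatible with a corrected analysis. The 9–18% then describes implementations that the reader has supplied. It is true that a corrected analysis is not ruled out. But the Protocol goes beyond silence: it fixes a method and threshold for a three-against-three design and omits clinics from the sentence that governs the primary outcome. Following that text in either usual form gives a wrong p-value and interval.

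Other points stand in part:
- The range does not bound every option. A model-based exchangeable variance with the ICC truncated at zero gave about 6% in one continuous-outcome simulation at ICC 0.01 and 7.6% in another. That is not the usual robust GEE test, and without truncation the error was again well above 5% (12% and 18%).
- The 9% is for a single visit. Repeated visits raise it.
- The binary sentence may be elliptical, with clustering meant to carry over. In that case the 18% figure is the relevant one.
- Some corrections may not be available in SPSS 21.0; this was not checked. The two-stage analysis needs only an ordinary t test on six clinic values.

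**Conclusion.** The concern holds, and it affects the validity of the primary test. At a nominal 5%, the uncorrected clinic-level sandwich with a normal reference has a true error of about 18%. This barely depends on the ICC or the number of covariates. Treating the patient as subject gives about 9% at the plan's ICC for one visit and about 10–14% with three; this figure depends strongly on the ICC. A t(4) reference without a variance correction still gives 8–9%.

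The closed-form sandwich results assume equal clinics and an unadjusted continuous outcome, and the simulations agree for adjusted logistic models and unequal clinics. The 40% control rate, the covariate effects and the within-patient correlations are assumptions, not Protocol figures. If the trial really has four clinics, two per arm, the sandwich error rises to 30%, and a 2-df test with 54 patients per clinic (216 in all) has 48.9% power for 3 mmHg.

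**What to change.** For every outcome, including the control rate, base inference for the arm effect on between-clinic variation with 4 df, by one of:
- **(a)** a two-stage analysis: covariate-adjusted clinic means or proportions compared by a t test on 4 df; or
- **(b)** GEE with the clinic as cluster, a named bias-corrected sandwich and a t(4) reference. The correction must be named, because the choice matters: Kauermann-Carroll or a 6/4 variance factor gives about 5% here, while Mancl-DeRouen with t(4) gives about 2%.

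State clinic clustering in the sentence on dichotomous outcomes. Reconcile four with six clinics and set the degrees of freedom from the reconciled number.

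**Cost.** This changes only analysis wording, and the 3 mmHg target needs no extra patients: the 4-df test keeps 80.7% power at SD 5, ICC 0.01 and 36 per clinic. The price is intervals about 1.7 times as wide as with the uncorrected sandwich and z.

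That power does not transfer to the primary outcome, for which the Protocol states no control-rate assumption. If usual-care control is assumed to be 30–50%, the 4-df test has about 50% power for a 20-point difference (0.517, 0.501 and 0.517 at 30%, 40% and 50%). It reaches 80% only at about 27–28 points. No 80% power should be claimed for the control rate unless the sample size is redone on that outcome.

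### Within-group p-values for BP control and mean BP cannot tell a programme effect from selection of uncontrolled patients and usual care

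*Protocol*

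**What the plan says.** **Analysis (Protocol, Data analysis).** The lead sentence is: "Primary analysis will be an intention-to-treat analysis of the difference in outcomes between groups at 6-18 months after baseline". Two sentences on generalized estimating equations (GEE) follow. The identity-link model is there "to assess differences in continuous outcomes within-group and between groups, adjusting for baseline patients' characteristics and clustering of patients per practice". For binary outcomes, "Generalized estimating equation models using logistic link will be conducted to analyze differences within-group and between groups for dichotomous outcomes". One rule closes the section: "P-value less than 0.05 will be considered statistically significant". It does not distinguish within-group from between-group results, and neither kind is called descriptive.

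**Selection (Research Subjects Recruitment).** Patients must be on treatment "with uncontrolled hypertension and no previous HBPM on the day of recruitment". The cut-off is above 140/90 mmHg, or above 150/90 from age 80. No confirmatory qualifying visit is described. Baseline Assessment describes three readings at one sitting, with the last two averaged.

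**Outcome and comparator.** BP control rate is the primary outcome. Under Usual Care, control patients have routine BP checks, medication changes at the professional's discretion, and nurse counselling.

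**Research Questions.** Question 1 asks whether control is higher after the device and education are provided. Question 2 asks: "Are there improvements in the clinic BP body weight, BMI, biochemical markers followed by the HBPM education program". Neither names usual care as the comparator.

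**The concern.** Patients enter because the variable that defines the primary outcome is abnormal. If the qualifying reading is the baseline, nobody is controlled at baseline and the control rate can only rise. Some patients qualify because their reading happened to be high that day, so later readings fall on average with no intervention. Usual care also acts on BP in both arms. A within-arm test from baseline to follow-up combines these influences with any programme effect and cannot separate them.

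What is at stake is the conclusion. Read literally, research questions 1 and 2 are before-after questions, and the within-group p-values would appear to answer them. A report could state that control improved significantly after the programme while the comparison with usual care shows nothing.

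There is also a technical point. If the qualifying reading is entered as a baseline outcome row in the logistic GEE, the baseline proportion is exactly 0, its log-odds is minus infinity, and the within-group odds ratio is not finite.

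**Working it through.** The protocol gives no figure for within-group change, so there is nothing to reproduce on this point. Its evaluable sample of 216 in six clinics, three per arm, gives 3 × 36 = 108 per arm, which is used below.

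**1. How few patients make a within-arm test significant.** Starting from 0 of 108 controlled, all changes go one way. With x patients controlled later, the exact McNemar p-value is 2 × 0.5^x.
- x = 5: p = 0.0625
- x = 6: p = 0.031

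So 6/108 = 5.6% is enough. McNemar stands in here for the planned covariate-adjusted GEE.

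**2. Regression to the mean with no programme effect and no treatment change.** Let qualifying and follow-up systolic readings be bivariate normal with the same mean μ and SD σ and with correlation ρ, and select on a first reading above 140. Put a = (140 − μ)/σ and λ = φ(a)/[1 − Φ(a)].
- Expected fall = (1 − ρ) σ λ
- Proportion at or below 140 at follow-up = [Φ(a) − Φ₂(a, a; ρ)] / [1 − Φ(a)]

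The protocol gives no μ or ρ, and its SD of 5 mmHg belongs to the sample size calculation. All three are therefore assumptions and are varied.

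Worked cases:
- μ = 140, σ = 5, ρ = 0.7: a = 0, λ = 0.798; fall = 0.3 × 5 × 0.798 = 1.2 mmHg. Φ₂ = 0.25 + arcsin(0.7)/(2π) = 0.3734; controlled = (0.5 − 0.3734)/0.5 = 25%.
- μ = 135, σ = 5, ρ = 0.5: a = 1, λ = 1.525; fall = 0.5 × 5 × 1.525 = 3.8 mmHg; controlled = (0.8413 − 0.7452)/0.1587 = 61%.
- μ = 135, σ = 10, ρ = 0.5: a = 0.5, λ = 1.141; fall = 0.5 × 10 × 1.141 = 5.7 mmHg; controlled 47%.
- μ = 145, σ = 5, ρ = 0.9: a = −1, λ = 0.288; fall = 0.1 × 5 × 0.288 = 0.14 mmHg; controlled 5%.

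**3. Chance that both arms reach p < 0.05 with no programme effect** (108 per arm; exact McNemar for control rate, z test for mean systolic BP; clustering ignored).

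| μ | σ | ρ | Fall (mmHg) | Controlled | Both arms, control rate | Both arms, mean BP |
|---|---|---|---|---|---|---|
| 140 | 5 | 0.7 | 1.2 | 25% | >0.99 | 0.85 |
| 140 | 5 | 0.5 | 2.0 | 33% | >0.99 | 0.99 |
| 135 | 5 | 0.5 | 3.8 | 61% | >0.99 | >0.99 |
| 140 | 10 | 0.7 | 2.4 | 25% | >0.99 | 0.85 |
| 135 | 10 | 0.5 | 5.7 | 47% | >0.99 | >0.99 |
| 140 | 10 | 0.9 | 0.8 | 14% | >0.99 | 0.22 |
| 145 | 10 | 0.9 | 0.5 | 9% | 0.88 | 0.05 |
| 145 | 5 | 0.8 | 0.3 | 7% | 0.65 | 0.02 |
| 145 | 5 | 0.9 | 0.1 | 5% | 0.23 | 0.01 |

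For scale, the design's target difference is 3 mmHg. In simulations of the same kind the between-arm test kept a type I error of 0.047-0.055, which is nominal.

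**The case against.** **The primary analysis is between groups.** The protocol says so directly before the GEE sentences, and the sample size is built on the difference between intervention and controls. This stands. A reader might infer from the shared 0.05 threshold that within-group tests have equal standing, or that the main result is compromised. The documents support neither. Only the threshold is shared, and regression to the mean cancels between arms selected by the same rule.

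**A significant within-group result is not a type I error.** The null of that test is no change over time. If readings do fall, rejecting it is correct, so it would be wrong to say the error rate is close to 100%. This also stands. The fault lies in attributing the change to the programme.

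**The size depends on inputs the protocol does not give.** Correct. One might infer that both arms are bound to look significant. That is nearly so for control rate in most scenarios, but for mean BP the chance runs from about 0.01 to above 0.99. The model also ignores the diastolic limit and the higher cut-off from age 80. Carrying baseline values forward for dropouts would dilute the change.

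**The baseline may not be the qualifying reading.** Patients are identified at a normal consultation, and a standardised baseline measurement is described separately. If the two differ, some regression happens before baseline. In the model with mean 135-140 and SD 5-10, even a correlation of 0.9 leaves about 14-27% controlled at a separate reading, and the odds ratio is then finite. Nor does the protocol say that baseline is an outcome row. The infinite odds ratio is therefore conditional. Usual care would still move both arms.

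**The research questions sit in a randomised trial whose aim speaks of comparing.** That before-after tests would be used to answer them is an inference. Their wording nevertheless invites it, and the analysis section supplies the tests.

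**Conclusion.** The concern holds for control rate and BP as a limit on interpretation. The stated within-group tests at p < 0.05 cannot separate a programme effect from selection on high BP and from usual care, and nothing marks them as descriptive. Under an assumed mean of 135-140 mmHg, SD 5-10 and correlation 0.5-0.7, selection alone produces an apparent control rate of about 25-61% and a fall of 1.2-5.7 mmHg. At its upper end that fall exceeds the 3 mmHg the trial is designed to detect. Under a mean of 145 or a correlation of 0.9 the artefact shrinks, at the extreme to about 5% and 0.1 mmHg. These figures assume that the qualifying reading serves as baseline and that selection is on systolic BP only.

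The point does not reach the primary between-group test, its error rate or the sample size. It does not extend directly to weight or biochemistry, which are not selection variables, although question 2 names them as well. A non-finite odds ratio arises only if the qualifying reading is a baseline outcome row.

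**What to change.** 1. In the two GEE sentences, remove within-group significance tests for control rate and BP. Report within-arm change descriptively, with confidence intervals and no p-values.
2. State that the logistic GEE for control rate uses follow-up visits only as the outcome.
3. Reword research questions 1 and 2 as comparisons with usual care, and state that conclusions rest on the between-group contrast.

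The cost is wording, plus the loss of within-arm p-values. Sample size, data collection and the primary test stay as they are.
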